## **6.4. PHARMAKOKINETICS**

### **6.4.1. Pharmacokinetic Analyses**

The concentration of ATI-502 in the blood will be summarized for the treatment period at pre-dose (Visit 2) and approximately 12-hr post dosing at Visits 4, 6 and 9.

## **7. CHANGES IN THE PROTOCOL-SPECIFIED ANALYSES**

All analyses specified in the SAP are consistent with those specified in the protocol. Should any deviations from the analyses specified in the authorized statistical analysis plan arise, such deviations will be documented in the final clinical study report.

## 8. PROGRAMMING CONVENTIONS

- Page orientation, margins, and fonts: Summary tables, listings, and figures will appear in landscape orientation. There should be a minimum of a 1” boundary on the upper (bound) edge, and a minimum of a 1.0” boundary on the remaining three edges. Output should be printed in Courier New with a point size of 8. Titles may be printed using a larger font (e.g., Arial point size 10).
  - Identification of analysis population: Every summary table and figure should clearly specify the analysis population being summarized. Listings will be prepared for all subjects.
  - Group headers: In the summary tables, the group headers will identify the summary group and the sample size for the indicated analysis population. Of note, the header’s sample size does not necessarily equal the number of subjects summarized within any given summary module; some subjects in the analysis population may have missing values and thus may not be summarized.
  - Suppression of percentages corresponding to null categories: When count data are presented as category frequencies and corresponding percentages, the percent should be suppressed when the count is zero in order to draw attention to the non-zero counts.
  - Presentation of sample sizes: Summary modules should indicate, in one way or another, the number of subjects contributing to the summary statistics presented in any given summary module. As mentioned above, this may be less than the number of subjects in the analysis population due to missing data.
    - In the quantitative modules describing continuous variables (and thus presenting sample size, means, and standard deviations), the sample size should be the number of non-missing observations. The number of missing observations, if any, will be noted.
    - For categorical variables that are presented in frequency tables, the module should present the total count in addition to the count in each category. Percentages should be calculated using this total as the denominator, and the percentage corresponding to the sum itself (that is, 100%) should be presented to indicate clearly to a reviewer the method of calculation. The number of missing observations, if any, will be noted.
  - Sorting: Listings will be sorted by treatment group, subject number and date, if applicable.
  - General formatting rules: Rounding for all variables will occur only as the last step, immediately prior to presentation in listings, tables, and figures. No intermediate rounding will be performed on derived variables. The standard rounding practice of rounding numbers ending in 0-4 down and numbers ending in 5-9 up will be employed.
  - Numerical Values: The presentation of numerical values will adhere to the following guidelines:
    - Raw measurements will be reported to the number of significant digits as captured electronically or on the CRFs.
-

- Standard deviations will be reported to two decimal places beyond the number of decimal places the original parameter is presented.
- Means will be reported to one decimal place beyond the number of significant digits as the parameter.
- Dates will be formatted as DDMMYYYY. Partial dates will be presented on data listings as recorded on CRFs.
- Time will be presented according to the 24-hour clock (HH:MM).

## 9. PROPOSED TABLES, LISTINGS, AND FIGURES

### Section 14.1 Accountability and Baseline Characteristics

1. Table 14.1.1 Subject Disposition and Reasons for Early Termination, ITT Population
2. Table 14.1.2 Primary Protocol Violations, ITT Population
3. Table 14.1.3 Analysis Populations, ITT Population
4. Table 14.1.3.1 Reasons for Exclusion from Per Protocol Population, ITT Population
5. Table 14.1.4 Demographics, ITT Population
6. Table 14.1.5 Baseline Characteristics, ITT Population
7. Table 14.1.6 Previous Therapies for Alopecia, ITT Population
8. Table 14.1.7 Medical History, ITT Population
9. Table 14.1.8 Physical Examination at Screening, ITT Population
10. Table 14.1.9.1 Prior Medications Safety Population
11. Table 14.1.9.2 Concomitant Medications Safety Population
12. Table 14.1.10 Study Medication Exposure and Compliance Safety Population

### Section 14.2 Efficacy

#### SALT

13. Table 14.2.1.1 Summary of SALT Score, Change from Baseline, and Percent Change from Baseline by Visit (LOCF), ITT Population
14. Table 14.2.1.1a Summary of SALT Score, Change from Baseline, and Percent Change from Baseline by Visit (Observed), ITT Population
15. Table 14.2.1.2 Analysis of Percent Change from Baseline in SALT Score (LOCF), ITT Population
16. Table 14.2.1.3 Analysis of Percent Change from Baseline in SALT Score (LOCF), PP Population
17. Table 14.2.1.4 Analysis of Percent Change from Baseline in SALT Score (Observed), ITT Population
18. Table 14.2.1.5 Analysis of Percent Change from Baseline in SALT Score (Observed), PP Population
19. Table 14.2.1.6 Analysis of Change from Baseline in SALT Score (LOCF), ITT Population

#### ALODEX

20. Table 14.2.2.1 Summary of ALODEX Score, Change from Baseline, and Percent Change from Baseline by Visit (LOCF), ITT Population
21. Table 14.2.2.2 Analysis of Percent Change from Baseline in ALODEX (LOCF), ITT Population
22. Table 14.2.2.3 Analysis of Change from Baseline in ALODEX Score (LOCF), ITT Population

### Responder Endpoints

23. Table 14.2.3.1 Proportion of Subjects Achieving  $\geq 50\%$  Hair Regrowth Based on SALT Score, ITT Population
24. Table 14.2.3.2 Proportion of Subjects Achieving  $\geq 50\%$  Hair Regrowth Based on ALODEX Score, ITT Population
25. Table 14.2.3.3 Proportion of Subjects Achieving an Absolute SALT Score  $\leq 10$ , ITT Population
26. Table 14.2.3.4 Proportion of Subjects with  $\geq 2$  Point Improvement in Scalp-ClinRO for Target Patch, AAP Subjects, ITT Population
27. Table 14.2.3.5 Proportion of Subjects with  $\geq 1$  Point Improvement in Scalp-ClinRO for Entire Scalp, ITT Population
28. Table 14.2.3.6 Proportion of Subjects with  $\geq 2$  Point Improvement in Scalp-PRO for Target Patch, AAP Subjects, ITT Population
29. Table 14.2.3.7 Proportion of Subjects with  $\geq 1$  Point Improvement in Scalp-PRO for Entire Scalp, ITT Population

### Scalp-ClinRO and Scalp-PRO

30. Table 14.2.4.1 Analysis of Change from Baseline in Scalp-ClinRO for Target Patch, AAP Subjects, ITT Population
31. Table 14.2.4.2 Analysis of Change from Baseline in Scalp-ClinRO for Entire Scalp, ITT Population
32. Table 14.2.4.3 Analysis of Change from Baseline in Scalp-PRO for Target Patch, AAP Subjects, ITT Population
33. Table 14.2.4.4 Analysis of Change from Baseline in Scalp-PRO for Entire Scalp, ITT Population

### PhGIS and SGIS

34. Table 14.2.5.1 Analysis of Change from Baseline in Physician Global Impression of Severity (PhGIS), AAP Subjects, ITT Population
35. Table 14.2.5.2 Analysis of Change from Baseline in Physician Global Impression of Severity (PhGIS), AU/AT Subjects, ITT Population
36. Table 14.2.5.3 Analysis of Change from Baseline in Subject Global Impression of Severity (SGIS), AAP Subjects, ITT Population
37. Table 14.2.5.4 Analysis of Change from Baseline in Subject Global Impression of Severity (SGIS), AU/AT Subjects, ITT Population

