### 2.4. Secondary Efficacy Endpoints

- Mean percent change from Baseline in the Alopecia Density and Extent Score (ALODEX) score at Week 24.
- Change from Baseline in the SALT score at Week 24 (Visit 9) with additional analyses at each applicable post-baseline visit where data are available.
- Change from Baseline in the Alopecia Density and Extent Score (ALODEX) score at Week 24 (Visit 9) with additional analyses at each applicable post-baseline visit where data are available.
- Proportion of subjects in each treatment arm achieving at least a 50% reduction in ALODEX score at Week 24 (Visit 9) with additional analyses at each applicable post-baseline visit where data are available compared to Baseline.
- Proportion of subjects in each treatment arm achieving at least a 50% reduction in SALT score at Week 24 (Visit 9) with additional analyses at each applicable post-baseline visit where data are available compared to Baseline.
- Change from Baseline in the Alopecia Scalp Appearance Assessment (ASAA) (Patient-reported outcome [PRO]) at Week 24 (Visit 9) with additional analyses at each applicable post-baseline visit where data are available.
- Change from Baseline in the Alopecia Scalp Appearance Assessment (ASAA) (Clinician-reported outcome [ClinRO]) at Week 24 (Visit 9) with additional analyses at each applicable post-baseline visit where data are available.
- Change from Baseline in the Physician Global Impression of Severity (PhGIS) at Week 24 (Visit 9) with additional analyses at each applicable post-baseline visit where data are available.

- Change from Baseline in Alopecia Facial Hair Appearance Assessment (AFHA) (Clinician and Subject) at Week 24 (Visit 9) with additional analyses at each applicable post-baseline visit where data are available.
- Change from Baseline in the Subject Global Impression of Severity (SGIS) at Week 24 (Visit 9) with additional analyses at each applicable post-baseline visit where data are available.
- Change from Baseline in the subject reported Alopecia Impact Assessment (AIA) at Week 24 (Visit 9) with additional analyses at each applicable post-baseline visit where data are available.
- Subject Global Impression of Treatment Satisfaction (SGITS) at Week 24 (Visit 9) with additional analyses at each applicable post-baseline visit where data are available.

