#### **Treatment Assignment:**

A total of approximately 95 subjects will be randomized in a 1:1:1:1 ratio:

- Placebo Oral Suspension, twice daily (BID) for 24 weeks (6 months)
- ATI-501 Oral Suspension, 400 mg, BID for 24 weeks (6 months)
- ATI-501 Oral Suspension, 600 mg, BID for 24 weeks (6 months)
- ATI-501 Oral Suspension, 800 mg, BID for 24 weeks (6 months)

During the screening period, subjects will be assessed for eligibility into the study. Subjects will receive ATI-501 Oral Suspension, 400 mg, 600 mg, or 800 mg or Placebo Oral Suspension twice-daily for up to 24 weeks. Assessment of response to treatment will be performed at Week 4 (Visit 4), Week 8 (Visit 5), Week 12 (Visit 6), Week 16 (Visit 7), Week 20 (Visit 8), Week 24 (Visit 9), and post-treatment (Visit 10). Safety and tolerability will be evaluated at each study visit by assessment of adverse events (AEs), clinical lab tests, vital signs, and at select visits, ECGs. The primary analysis will be conducted after all subjects complete Visit 9 or Visit 10.

Subjects who complete Visit 9 (Week 24) will be eligible to enter a 28-week open-label study ATI-502-AA-203. Subjects who decline or are not eligible for ATI-502-AA-203 should be seen for the Visit 10 (Post-treatment) assessments.

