## **4. GENERAL STATISTICAL CONSIDERATIONS**

### **4.1. SAMPLE SIZE AND POWER**

The planned sample size is 95 enrolled subjects with approximately 45 subjects enrolled with AT or AU. It is assumed that the proportion of subjects who achieve at least a 50% reduction in hair loss (SALT50) for the pooled 600mg and 800mg treatment groups will be at least 32%, and the SALT50 for the pooled placebo and 400mg treatment groups will be at most 6%. Assuming a 10% dropout rate, this results in >80% power for the SALT50 analysis. Because the primary efficacy analysis of mean percent change in hair loss using SALT scores is expected to be more sensitive than the SALT50 responder analysis, the power for the primary analysis is also expected to be no less than 84%.

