## **6. STATISTICAL METHODS**

Descriptive statistical methods will also be used to summarize the data from this study, with hypothesis testing performed for the primary and key secondary efficacy endpoints. Unless stated otherwise, the term “descriptive statistics” refers to number of subjects, mean, median, standard deviation, minimum, and maximum for continuous data, and frequencies and percentages for categorical data. For categorical variables, the denominator of percentages will be the number of subjects in the treatment group, except for those collected by study visit and/or scheduled time point, in which case the denominator of percentages will be the number of subjects with a non-missing value at the visit and/or the scheduled time point. If a different denominator is used, this will be identified in the summary table.

All data collected during the study will be included in data listings. Unless otherwise noted, the data will be sorted first by treatment group, subject number, and then by date within each subject number.

The term ‘treatment group’ refers to ATI-501 active groups and matching Placebo Oral Suspension group.

All statistical testing will be two-sided and will be performed using a significance (alpha) level of 0.05 unless otherwise stated. P-values will be presented to three decimal places. For the efficacy

endpoints, the ATI-501 treatment groups will be tested versus Placebo Oral Suspension via statistical inference.

The statistical analyses will be conducted with the SAS® software package version 9.4 or higher. All analyses will be subject to formal verification procedures. Specifically, results will be independently verified by a second programmer/statistician prior to issuance of the draft statistical report. All documents will be reviewed by the lead statistician to ensure accuracy and consistency.

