#### **6.2.5. Secondary Efficacy Analysis**

Descriptive statistics will be presented for all secondary efficacy endpoints.

The mean percent change from baseline in the ALODEX score (percent regrowth); the mean change from baseline in SALT and the mean change from baseline in ALODEX will be analyzed using the methods planned for the primary efficacy analysis. The calculated DLQI total score ranges from 0 to 30. This mean change from baseline in DLQI will also utilize the MMRM analysis as planned for the primary efficacy analysis.

Responder-type analyses are planned based on the SALT, ALODEX, Scalp-ClinRO, and Scalp-PRO. The responder definitions include:

- The proportion of subjects achieving a  $\geq 50\%$  hair regrowth compared with baseline for SALT and for ALODEX scores
- Proportion of subjects achieving an absolute SALT score  $\leq 10$
- Proportion of subjects with  $\geq 2$ -point improvement in Scalp-ClinRO for the Target Area (patchy AA subjects only)
- Proportion of subjects with  $\geq 2$ -point improvement in Scalp-PRO for the Target Area (patchy AA subjects only)
- Proportion of subjects with  $\geq 1$ -point improvement in Scalp-ClinRO for the entire scalp
- Proportion of subjects with  $\geq 1$ -point improvement in Scalp-PRO for the entire scalp

The observed proportion of responders and associated 95% CI will be presented. Adjusted rates and 95% CI will be obtained from a logistic regression model with a factor for treatment. The p-value for the overall global test that  $\beta=0$  for this factor will be presented. The adjusted odds ratios (95% CI) for being a responder (active/placebo oral suspension) will be presented along with the associated p-value.

The questionnaires Scalp-PRO, Scalp-ClinRO, PhGIS, AFHA, and SGIS are collected on a 1-5 scale. The SGRHQ questionnaire is collected on a 1-7 scale. The frequency of responses for each value will be reported by visit and treatment group. Additionally, change status will be categorized as “Better by x points” when the score decreases from baseline by x points, and as “Worse by x points” when the score increases by x points. For these scales, a Wilcoxon rank sum test will be used at each visit to obtain a p-value to compare the change status of each active treatment group to the placebo oral suspension.

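### The SAP table list analyses PhGIS and SGIS only within the patchy and AT/AU forms, with no comparison in all ITT subjects; a form-stratified test should be added

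*SAP*

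**What the plan says.** Protocol 2.4 gives each scale one entry; the first reads "Change from Baseline in the Physician Global Impression of Severity (PhGIS) at Week 24 (Visit 9"), and SGIS is worded the same way. SAP 6.2.4 keeps the patchy (AAP) and AT/AU forms of each scale in one bullet. SAP 5.1 applies the ITT population to all efficacy analyses.

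SAP 6.2.5 treats PhGIS and SGIS as single scales scored 1 to 5 and states: "For these scales, a Wilcoxon rank sum test will be used at each visit to obtain a p-value to compare the change status". The contrast is active dose against placebo, and the text names no subgroup.

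SAP 9 lists four analysis tables for these scales, from "Table 14.2.5.1 Analysis of Change from Baseline in Physician Global Impression of Severity (PhGIS), AAP Subjects, ITT Population" to "Table 14.2.5.4 Analysis of Change from Baseline in Subject Global Impression of Severity (SGIS), AU/AT Subjects, ITT Population". Each covers one form, and no table covers all subjects.

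Other paired forms are pooled. The clinician whole-scalp rating appears as "Table 14.2.4.2 Analysis of Change from Baseline in Scalp-ClinRO for Entire Scalp, ITT Population", and the list has matching all-subject tables for Scalp-PRO (14.2.4.4) and for SGSHQ entire scalp (14.2.7.2).

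SAP 6.2.5 also plans a stratified Wilcoxon test for SGITS, PhGIC and SGIC without naming the strata, whereas SAP 4.3.1 says that no stratified analyses are planned.

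**The concern.** If the table list is followed, no output gives one comparison of a dose with placebo for PhGIS or SGIS in the randomised population. The reader gets two p-values per scale, each from about half the trial, and no rule for reading them when they disagree. A real effect of moderate size would often be missed in one half or both. Taking either half as evidence raises the false-positive rate.

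The existence of two forms does not by itself explain the split. The two PhGIS forms (Protocol 7.3.4.1 and 7.3.4.2) differ only in the disease named and share five response levels; the SGIS forms (Appendices 5 and 11) do the same. SGSHQ is pooled although its wording differs more: Appendix 8 asks about all treated patchy areas, and Appendix 13 asks about the scalp.

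**Working it through.** **The plan's own power figure.** None is stated for PhGIS or SGIS. The only stated power is for SALT50, 32% v 6% in two pooled groups: over 80%, with at least 84% carried over to the primary analysis. With 95/2 × 0.9 = 42.75 per group I get 87.9% (normal approximation) and 81.0% (continuity-corrected). Fisher's exact test at 43 v 43 gives 84.4%. The stated figures are reproduced, but they do not bear on these two scales.

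**Sample size per test.** Inputs: "The planned sample size is 95 enrolled subjects with approximately 45 subjects enrolled with AT or AU" (SAP 4.1) and "A total of approximately 95 subjects will be randomized in a 1:1:1:1 ratio" (SAP 1.1). I assume that the other subjects are patchy, 95 − 45 = 50, and that diagnosis falls evenly across arms.
- All subjects: 95/4 = 23.75 per arm
- Patchy: 50/4 = 12.5 per arm
- AT/AU: 45/4 = 11.25 per arm

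With the SAP's 10% dropout, these become 21.4, 11.25 and 10.1.

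**Power on a normal scale.** The level comes from SAP 6: "All statistical testing will be two-sided and will be performed using a significance (alpha) level of 0.05 unless otherwise stated". Power = Φ(d√(n/2) − 1.96), where d is the standardised difference, assumed equal in both forms. At d = 0.8:
- All: 0.8 × √11.875 − 1.96 = 0.797, power 79%
- Patchy: 0.8 × √6.25 − 1.96 = 0.040, power 52%
- AT/AU: 0.8 × √5.625 − 1.96 = −0.063, power 47%

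| d | All | Patchy (ratio to all) | AT/AU (ratio to all) |
|---|---|---|---|
| 0.3 | 18% | 11% (0.64) | 11% (0.60) |
| 0.5 | 41% | 24% (0.59) | 22% (0.54) |
| 0.8 | 79% | 52% (0.66) | 47% (0.60) |
| 1.0 | 93% | 71% (0.76) | 66% (0.71) |
| 1.2 | 99% | 85% (0.86) | 81% (0.82) |

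The relative loss is therefore about 35–46% for d from 0.3 to 0.8, and smaller above that. The effect detectable with 80% power, (1.96 + 0.84)√(2/n), is d = 0.81 in all subjects, 1.12 in patchy and 1.18 in AT/AU.

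**Ordinal check.** I simulated 12 v 12 in each form. The form-specific test is a tie-corrected Wilcoxon. The combined test is van Elteren: rank within form, weight each form by 1/(N+1), and sum. The distributions of 0/1/2/3-point improvement are assumptions.
- Scenario 1: placebo 80/15/5/0%, active 50/20/20/10%
- Scenario 2: placebo 75/20/5/0%, active 40/25/20/15%

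| Same effect in both forms | One form-specific test | Either form significant | Combined test |
|---|---|---|---|
| Scenario 1 | 38% | 62% | 70% |
| Scenario 2 | 51% | 76% | 83% |

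These are from 8,000 runs; a repeat with 20,000 agreed to about one point. The relative losses are 1 − 38/70 = 46% and 1 − 51/83 = 39%. Exactly one form was significant in 47–50% of trials, although the true effect was the same in both.

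**Type I error.** Under the null the combined test rejected in about 5% of trials. Reading either form gives at most 1 − 0.95² = 9.75%; in simulation it was about 8%, because the small-sample Wilcoxon is conservative.

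**Effect in one form only** (20,000 runs). In the form with the effect, the form-specific test has 39.5% power and the combined test 25.6% in scenario 1, a loss of 14 points. In scenario 2 the figures are 51.3% and 32.4%, a loss of 19 points.

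**The case against.** The case for leaving the plan as it is has four parts.

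First, SAP 9 is headed as proposed tables, and table titles do not settle which population is tested. SGITS is also tabulated by form, yet SAP 6.2.5 plans a stratified Wilcoxon for it. A reader might infer that PhGIS and SGIS are never to be tested in all randomised subjects. The documents do not go that far, because the methods text sets no restriction by form. This stands; what remains is a methods text and a table list that do not match.

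Second, a reader might infer that the split halves the chance of detecting an effect. It halves the sample size per test. The relative loss of power is nearer 40%, and the chance that at least one form is significant stays close to that of the combined test (75% v 79% at d = 0.8). This also stands, though that near-equality is bought with the higher type I error, and SAP 4.3.3 plans no adjustment.

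Third, the forms ask about different conditions, and Protocol 9.4.2 leaves the analysis of such parameters to the SAP, so reporting by form is permissible. That is fair, but it does not explain why SGSHQ is pooled. A stratified test also ranks within form and needs no equivalence between forms.

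Fourth, equal effects may be optimistic. Protocol 1.1 says spontaneous regrowth is common in patchy disease and rare in AT/AU, and an effect confined to one form costs the combined test 14–19 points. This stands, and is the reason not to demote the form-specific tests to description only.

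**Conclusion.** The point holds in a limited form. The table list gives no overall comparison for two endpoints that the protocol states as single endpoints, and it departs from how the SAP treats other paired forms. If the effect is similar in both forms, each listed test has about 35–46% less power in relative terms than one combined test for small to moderate effects, and less of a loss for large ones. This rests on assumed effect sizes, on even balance of diagnosis across arms (no stratified randomisation is described) and on similar effects in the two forms.

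The documents do not show that an overall test has been ruled out, nor that the form-specific tests are wrong to have. Priority is minor: these are two of many unadjusted secondary endpoints in a Phase 2 trial, no power is claimed for them, and the primary analysis does not depend on them.

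**What to change.** Before unblinding:
- In SAP 6.2.5, add for PhGIS and for SGIS one comparison of each dose with placebo in all ITT subjects, using a Wilcoxon test stratified by form (van Elteren; strata AAP and AT/AU). Add the two matching tables to SAP 9.
- Keep the four form-specific tables and their tests, labelled supportive.
- Correct SAP 4.3.1, which already conflicts with the stratified Wilcoxon planned in SAP 6.2.5 for SGITS, PhGIC and SGIC.

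The cost is two extra tables and no new data. The statistical price is the 14–19 points of power lost in these scenarios if only one form responds; the retained form-specific tests cover that case.
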